8.2 Safety Evaluation

8.2.1 Routine laboratory safety evaluation

Table 15. Routine laboratory safety evaluation

Hematology	RBC, HGB, HCT, WBC, PLT, LYM, ANC, MONO, EOS, and BASO
Coagulation Function	TT, PT, APTT, and INR
Clinical Chemistry	TBIL ^a , ALT, AST, γ -GT, ALP, ALB, TP, LDH, BUN, Cr, Na, K, Cl, Mg, Ca, P, lipase, amylase, and FBG
Urinalysis	PH, UALB, UPRO ^b , URBC ^c , and UGLU
Routine Stool Test	Occult blood

^a. If TBIL $\geq 2 \times$ ULN (without evidence of Gilbert syndrome), then direct bilirubin and indirect bilirubin shall be tested separately.

^b. The white blood cells should be examined microscopically (if appropriate), and the red blood cells should be examined with a high-power field of view.

8.2.2 Physical examination

A complete physical examination includes: general conditions, respiratory tract, cardiovascular system, abdomen, skin, head and neck (including ears, eyes, nose, and throat), lymph nodes, thyroid, musculoskeletal (including spine and limbs), genitals/anus, and nervous system evaluation.

Refer to the schedule of visits in [Table 1](#) for the time points of examinations. Refer to Appendix 1 for ECOG PS scoring criteria.

8.2.3 12-Lead ECG

The resting 12-lead ECG will be analyzed in the local laboratory according to the visit schedule.

The 12-lead ECG examination will be performed after the subject rests for at least 5 min in the lying position. All 12-lead ECGs should be recorded while the subject is lying and resting. When clinically needed, for example when a cardiac AE is noted, further ECG examinations will be

performed. On the day of the examination, the investigator completes the ECG assessment and records the assessment results on the electrocardiogram. The same assessment method should be used throughout the study period.

The ECG will be recorded at a speed of 25 mm/s. The investigator should evaluate all ECGs based on clinically significant abnormalities/clinically non-significant abnormalities. The investigator should record clinically significant abnormal findings as AEs in the eCRF.

8.2.4 Vital signs

Vital signs will be measured as described in the study visit schedule. Vital signs include body temperature, pulse rate, respiratory rate, and blood pressure.

The investigator may perform additional vital sign assessment and monitoring according to standard clinical practice or based on clinical needs.

In the event of an AE/SAE, additional vital sign records may be collected on the eCRF (if applicable). The date and time of collection and measurement will be recorded in the appropriate section of the eCRF.

8.2.4.1 Pulse and blood pressure

Pulse and blood pressure are measured during the screening period and before the scheduled SHR-1210 infusion.

Blood pressure monitoring: cigarettes and caffeine are prohibited within 30 min before each blood pressure measurement, and subjects shall rest for at least 10 min. The blood pressure will be measured at sitting position with elbow on the same level as heart. All measurements should be taken on the same side.

During the screening period and before each scheduled SHR-1210 infusion, the investigator will measure the blood pressure of the subject. During the study, the subject will monitor the blood pressure and record on the diary card. Blood pressure shall be measured at least 3 times per week in the first 2 cycles. For subjects with abnormal blood pressure, the blood pressure shall be measured daily; if normal, the blood pressure shall be measured twice per week after Cycle 2.

8.2.4.2 Body temperature and respiration

Body temperature and respiration are measured during the screening period and before the scheduled SHR-1210 infusion.

8.2.5 Weight and height

Height will be measured only during the screening period. Weight will be measured during the screening period, before SHR-1210 administration at each visit, at the end of the treatment, and at safety follow-ups.

8.2.6 Pregnancy test

Women of childbearing potential undergo a serum human chorionic gonadotropin (hCG) pregnancy test within 3 days before the first dose of the study drug. Subjects with a positive result are not eligible or must discontinue participation in the study. Retests will be performed when pregnancy is suspected during the study period.

8.2.7 Other safety examinations

- Hepatitis B tests: HBsAg, HBsAb, HBcAb, HBeAg, and HBeAb.
- HIV antibodies and HCV antibodies
- Thyroid function: T3, T4, TSH, FT3, and FT4
- Myocardial zymography: LDH, AST, CK, CK-MB, and ALT
- Pituitary adrenal axis test: Including tests of CRH, plasma ACTH, and adrenocortical hormone. Adrenocortical hormone tests include serum cortisol, UFC, 17-KS, and 17-KGS
- Echocardiography
- Pulmonary function test: maximum vital capacity, the forced expiratory flow at 25-75% of forced vital capacity (FEF25-75), the peak expiratory flow rate (PEF), the maximum expiratory volume per second, diffusing capacity of the lungs for carbon monoxide (DLCO) and oxygen saturation, which will be performed during the screening period and based on clinical indicators as determined by the investigator thereafter. Subject to the actual conditions of each site.
- Arterial blood gas test: optional. This test includes partial arterial pressure of oxygen (PaO₂), partial arterial pressure of carbon dioxide (PaCO₂), arterial oxygen saturation (SaO₂), and pH, and can be performed during the screening period. Subject to the actual conditions of each site.

8.3 Pharmacokinetics

Not applicable.

8.4 Pharmacodynamics

Not applicable.

8.5 Immunogenicity

Immunogenicity blood samples will be collected once within 0.5 h before SHR-1210 infusion on D1 of cycle 1, cycle 2, and the third cycle of every three cycles thereafter (cycles 5, 8, 11, etc.), once at the end of the treatment, and once per month at safety follow-ups after withdrawal for

3 times (if applicable). In case of national holidays, the blood collection time may be adjusted as appropriate. If the subject develops SHR-1210-related infusion reactions, blood samples should be collected as close as possible to the onset of the event, to the end of the event, and about 30 days after the end of the event, for immunogenicity comparison and analysis. Immunogenicity blood samples should be collected following the study protocol. However, if deemed necessary by the investigator, unscheduled immunogenicity blood samples may be collected.

Each subject shall be tested for anti-drug antibody (ADA) titer. ADA-positive serum samples will be further tested for neutralizing antibodies (NAb). Four (4) mL of blood will be collected each time for immunogenicity. Please refer to the Laboratory Manual provided by the sponsor-designated central laboratory for sampling methods, sample storage, transportation, and analysis.

8.6 Biomarker Analysis

Subject to the permission of the ethics committee, all subjects who meet the inclusion criteria shall provide diagnostic tumor tissues at baseline. Acceptable tumor tissues include 5-10 unstained 4-6 μ m slices prepared with archived tumor tissues or freshly obtained during the screening period.

After the subject's ICF is obtained and after the study medication, another biopsy is preformed before PD or treatment discontinuation to provide tumor tissue to the central laboratory for testing and analysis of the relationship between the change in PD-L1 expression before and after the administration and the efficacy. These samples may also be used for exploratory biomarker analysis, including but not limited to PD-L1 expression.

After the subject's ICF is obtained, about 16 mL of peripheral blood may be collected for tumor biomarker detection during the screening period, at each tumor evaluation, and the end of the treatment.

Refer to the Laboratory Manual for sample processing, handling, and transportation.

8.7 Storage and Destruction of Biological Samples

The samples will be disposed of or destroyed, and pooled and anonymized. Additional analysis may be performed on the anonymized and pooled samples to further evaluate and validate the analysis method. Any results obtained from these analyses may be reported separately from CSR.

The sample reproducibility analysis (if performed) will be performed simultaneously with the biological sample analysis. These evaluation results will not be reported in the clinical study report, but will be separately given in a biological sample analysis report.

9 SAFETY EVALUATION

9.1 AE

9.1.1 Definition of AE

AE refers to any untoward medical condition in a clinical study subject who receives a pharmaceutical product, and the condition does not necessarily have a causality with the treatment. All AEs from signing of the informed consent form to the end of the safety follow-up period (90 days after the last dose) or the start of other anti-tumor treatments will be collected in this study. AEs can include any unfavorable and unintended symptoms, signs, abnormal laboratory findings, or diseases, including the following:

- 1) Worsening of pre-existing (prior to entering the clinical trial) medical conditions/diseases (including worsening symptoms, signs, or laboratory abnormalities);
- 2) Any new AE: Any new adverse medical conditions (including symptoms, signs, and newly diagnosed diseases);
- 3) Clinically significant abnormal laboratory findings.

All AEs should be documented in detail by the study personnel, including: the name of the AE and description of all relevant symptoms, onset time, severity, causality assessment, duration, measures taken, as well as final results and outcomes.

9.1.2 AE severity grading criteria

Please refer to NCI CTCAE 4.03 for grading standards. Refer to the following criteria for AEs not listed in NCI-CTCAE 4.03:

Grade	Clinical Description of Severity
1	Mild; asymptomatic or mild clinical symptoms; clinical or laboratory test abnormality only; intervention not indicated.
2	Moderate; minimal, local, or non-invasive interventions required; limited age-appropriate instrumental activities of daily living (ADL), e.g., cooking, shopping, using the telephone, counting money.
3	Severe or medically significant symptoms but not immediately life-threatening; hospitalization or prolonged hospitalization indicated; disabling; limiting self-care ADL. Self-care ADL: refer to bathing, dressing and undressing, feeding self, using the toilet, taking medications, and not bedridden
4	Life-threatening consequences; urgent intervention indicated
5	Resulting in death

9.1.3 Causality assessment of AEs

AEs include all unexpected clinical manifestations. All such events occurring after the signing of the ICF must be reported as AEs regardless of whether they are related to the study drugs or even whether the subject has received the drugs. All subject complaints and abnormal changes in laboratory tests during the treatment period will be documented truthfully. The severity, duration,

measures taken, and outcome of the AE will be noted. The investigator shall assess the causality between the AE and the study drug, such as whether there is a plausible temporal relationship with the study drug, the characteristics of the study drug, the toxicological and pharmacological effects of the study drug, whether there are concomitant medications, the subject's underlying diseases, medical history, family history, as well as dechallenge and rechallenge. The potential relationship between the AE and the study drug will be assessed with 5 grades of causality: "definitely related", "possibly related", "unlikely related", "not related", and "indeterminable". Events deemed "definitely related", "possibly related", "unlikely related", and "indeterminable" will be listed as adverse drug reactions. When calculating the incidence of AEs, the total of these four categories shall be used as the numerator and the total number of subjects for safety assessments shall be used as the denominator.

9.2 Serious Adverse Event (SAE)

9.2.1 Definition of SAE

An SAE is any untoward medical occurrence at any dose. The following medical events are included:

- Events resulting in death;
- Life-threatening events (defined as when the subject is at immediate risk of death at the time of the event);
- Events resulting in hospitalization or prolonged hospitalization;
- Events resulting in permanent or serious disability/incapacity/impairment of work ability;
- Congenital anomalies or birth defects;
- Other important medical events (defined as events that may jeopardize the subject or require interventions to prevent any of the above).

9.2.2 Hospitalization

AEs that result in hospitalization (even if for less than 24 h) or prolonged hospitalization during the clinical study should be considered as SAEs.

Hospitalization does not include the following:

- Hospitalization at a rehabilitation institution
- Hospitalization at a sanatorium
- General emergency admission

- Day surgery (e.g., outpatient/same-day/ambulatory surgery)
- Social reasons (medical insurance reimbursement, etc.)

Hospitalization or prolonged hospitalization unrelated to the worsening of an AE is not an SAE.

For example:

- Hospitalization due to pre-existing disease without the occurrence of new AEs or worsening of the pre-existing diseases (e.g., in order to examine the persistent laboratory abnormalities that started before the study);
- Hospitalization for management reasons (e.g., annual physical examination);
- Hospitalizations during the study as specified in the protocol (e.g. hospitalization performed in accordance with study protocol);
- Elective hospitalization unrelated to worsening of AEs (e.g., elective surgery);
- Scheduled treatment or surgical procedures, which should be documented in the individual subject's baseline information;
- Hospitalization merely for use of blood products.

Diagnostic or therapeutic invasive (e.g., surgery) and non-invasive procedures should not be reported as AEs. However, when a condition resulting in such procedures meets the definition of AE, it should be reported as such. For example, acute appendicitis during the AE reporting period should be reported as an AE, and the resulting appendectomy shall be recorded as the treatment of the AE.

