3.2 Study Endpoints

3.2.1 Primary endpoints

- Incidence of AEs evaluated per CTCAE 4.03, especially the incidence of AEs meeting any of the following criteria:
 - Hematologic toxicity
 - Grade 4, or
 - Grade ≥ 3 thrombocytopenia with hemorrhage, or
 - Grade ≥ 4 neutropenia with pyrexia and infection
 - Grade ≥ 3 non-hematologic toxicity (except for laboratory abnormalities), hypertension, rash, diarrhea, nausea and vomiting that cannot be controlled after symptomatic treatment
 - Grade ≥ 3 laboratory abnormalities that lead to medical interventions or hospitalization, or last for ≥ 7 days
 - Any Grade 5 AEs
- ORR evaluated as per RECIST v1.1

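### Protocol 9.2.2 lists an undefined type of emergency admission as not being hospitalization, which can be read against its own rule that any hospitalization for an AE makes the event an SAE

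*Protocol*

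**What the plan says.** Protocol 9.2.1 gives six criteria for an SAE. One is "Events resulting in hospitalization or prolonged hospitalization". Another is "Other important medical events (defined as events that may jeopardize the subject or require interventions to prevent any of the above".

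Protocol 9.2.2 then expands on hospitalization in three steps.

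- The general rule: "AEs that result in hospitalization (even if for less than 24 h) or prolonged hospitalization during the clinical study should be considered as SAEs".
- A first list, headed "Hospitalization does not include the following". Its five items are stays in a rehabilitation institution, stays in a sanatorium, "General emergency admission", day surgery, and stays for social reasons.
- A second list, of examples under a different heading: "Hospitalization or prolonged hospitalization unrelated to the worsening of an AE is not an SAE". The last example is "Hospitalization merely for use of blood products".

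Protocol 9.2.6 requires the sponsor to be notified of an SAE within 24 hours. Protocol 3.2.2 names SAE incidence as a secondary endpoint. SAP 5.5.1 tabulates SAEs and does not define hospitalization again.

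**The concern.** The first list is a definition, and its heading carries no condition about the cause of the stay. Whatever is on the list is not hospitalization and so never reaches the general rule. A subject admitted as an emergency because of an AE is therefore an SAE under the opening sentence and not hospitalized under the list.

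Two things are at stake. One is the SAE count, which may be too low and may depend on which sentence a site follows. The other is expedited notification, which is triggered by SAE status. Hospitalization is meant to be the objective criterion. If it is unclear, an event may be reported only because an investigator judged it medically important.

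**Working it through.** No arithmetic applies. The documents give no expected SAE rate and no share of admissions that are emergencies. The check is to follow one type of event through the text.

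**1. The event.** A subject has an AE and is admitted as an inpatient through the emergency route for a short stay. The AE is not fatal, life-threatening or disabling, involves no congenital anomaly, and is not judged an important medical event.

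**2. Two answers from 9.2.2.**

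| Text applied | Is it hospitalization? | SAE? | 24-hour SAE notification (9.2.6)? |
|---|---|---|---|
| Opening sentence | Yes; length is irrelevant | Yes | Yes |
| First list, read literally | No; emergency admission is listed | No | No |

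**3. Does anything else settle it?** Section 9.2.1 repeats the hospitalization criterion without defining the word. Section 9.2.6 and SAP 5.5.1 take SAE status as given. The word *general* is not explained anywhere. The conflict therefore stays open.

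**4. What is still captured.**

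- Events that meet any other criterion in 9.2.1 remain SAEs.
- Potential drug-induced liver injury is reported as an SAE under 9.2.4, with no reference to admission.
- Grade 3 or higher infusion reactions and other Grade 3 or higher immune-related AEs go to the sponsor within 24 hours under 9.4, whatever their SAE status.
- All events are still collected and graded as AEs under 9.1.

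**5. What is exposed.** Only AEs whose sole seriousness criterion is the emergency admission. For SAE incidence counted by subject, a subject drops out only if every SAE that subject has is of this kind. The undercount thus lies between zero and the number of such subjects, and the documents do not let that number be estimated.

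**6. Primary safety endpoint.** One component in Protocol 3.2.1 covers Grade 3 or higher "laboratory abnormalities that lead to medical interventions or hospitalization", or abnormalities lasting at least 7 days. It does not require SAE status, and medical intervention or duration alone is enough. The ambiguity could reach only a laboratory abnormality that qualifies through hospitalization and nothing else.

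**7. The blood-product example.** It is in the second list, so its heading already limits it to stays unrelated to worsening of an AE. Two neighbouring examples repeat a condition of that kind; this one does not. Protocol 6.4.1 gives transfusion as the remedy that makes dose changes unnecessary for non-hemolytic anemia. An admission for transfusion can therefore follow from an on-study AE, and a site reading the example alone could misapply it.

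**The case against.** The best defence is that the first list only narrows a term, as definitions do. The other items are not acute inpatient stays for an AE, and an emergency-room attendance without admission would fit the series. On that reading there is no conflict. This may well be the intent, but the text does not say so: it uses the word admission, and the two items before it are stays in an institution. If that is the meaning, the proposed wording simply states it.

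Three parts of the defence do stand, each against a stronger reading that a reader might infer.

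- *That the section removes unplanned toxicity admissions from the SAE count.* It does not. The other criteria in 9.2.1 apply whatever the type of admission, and 9.2.4 and 9.4 give separate routes to the sponsor.
- *That admission for blood products is declared not to be hospitalization, so that admission for worsening anemia or thrombocytopenia is not an SAE.* The example is in the second list, and that list's heading leaves admissions for a worsening AE under the opening rule. Section 6.4.1 mentions transfusion for non-hemolytic anemia only.
- *That the bias in SAE incidence can be given a number.* Any percentage would rest on an SAE count and an emergency-admission share that the documents do not contain.

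**Conclusion.** Wrong as written: an internal inconsistency in a reporting definition. Section 9.2.2 gives opposite answers for an AE whose only seriousness criterion is an emergency inpatient admission, and neither document resolves it. If sites follow the list, the direction is toward too few SAEs and missed 24-hour SAE reports. If sites differ in which sentence they follow, SAE incidence will vary between centers for reasons unrelated to safety. The size is unknown.

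This conclusion rests on the literal reading of the list item. If every site takes it to mean an emergency-room visit without admission, nothing is lost, but the protocol does not ensure that. The affected measure is a secondary endpoint; ORR is untouched, and most of the primary safety endpoint is too. The blood-product example is a matter of clarity, not a second contradiction.

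**What to change.** In the first list of 9.2.2, replace the emergency item with: emergency-department visit without inpatient admission. The opening sentence then governs every inpatient admission for an AE.

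As a minor clarification, repeat the heading's condition on the blood-product example in the second list: it applies only when the admission for transfusion is not caused by a new or worsening AE.

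Both changes concern reporting only and leave treatment rules as they are. The cost is two lines of protocol text and a memo to sites. The downside is a slightly higher reported SAE rate and a few more SAE forms.

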9.2.3 Progressive disease

Progressive disease is defined as the worsening of the subject's conditions caused by the indications of the study, including radiological progressions and progressions in clinical symptoms and signs. New metastases relative to the primary tumor or progressions of the previous metastases are recognized as PD. Life-threatening events, hospitalization or prolonged hospitalization, or events resulting in permanent or severe disability/incapacity/impairment of work ability, congenital anomalies or birth defects arising from the symptoms and signs of PD are not reported as SAEs. Death caused by the symptoms and signs of PD will be reported as an SAE.

9.2.4 Potential drug-induced liver injury

Drug-induced liver injury will be considered if AST and/or ALT levels are abnormal accompanied with abnormal elevation of total bilirubin, the following criteria are met, and when there are no other causes of liver injury. These cases should always be considered as important medical events.

Potential drug-induced liver injury is defined as follows:

Baseline Period	Normal (AST/ALT and TBIL)	Abnormal (AST/ALT and TBIL)
Treatment Period	
ALT or AST $> 3 \times$ ULNwith TBIL $\geq 2 \times$ ULNand ALP $\leq 2 \times$ ULNand no hemolysis	
AST or ALT $\geq 2 \times$ baseline level, and values $\geq 3 \times$ ULN; or AST or ALT $\geq 8 \times$ ULNwith TBIL increase $\geq 1 \times$ ULN or TBIL $\geq 3 \times$ ULN

After being notified of the abnormal results, the subjects should return to the study center for an assessment as soon as possible (preferably within 48 h). Assessments include the laboratory tests, detailed medical history, and physical assessment, and the possibility of hepatic tumor (primary or secondary) should be considered.

Except for the reexaminations of AST and ALT, albumin, creatine kinase, TBIL, direct and indirect bilirubin, γ -GT, prothrombin time (PT)/international normalized ratio (INR), and ALP should also be examined. Detailed medical history should include history of alcohol use, acetaminophen, soft drugs, various supplements, family diseases, occupational exposure, sexual behavior, travel, contact with jaundice patients, surgery, blood transfusion, hepatic diseases, and allergies. Further tests may include the testing for acute hepatitis A, B, C and E, and hepatic imaging (such as biliary tract). If the above laboratory criteria are confirmed upon re-examination, the possibility of potential drug-induced liver injury should be considered in the absence of any other causes of abnormal liver function, without waiting for all liver function test results. Potential drug-induced liver injury should be reported as an SAE.

